Institution/Department : Kaohsiung Veterans General Hospital

Principal Investigator (PI) : [name]

Research Project Title : Comparing the efficacy and impact on gastrointestinal microbiome of reverse hybrid therapy and bismuth quadruple therapy in *Helicobacter pylori* eradication

NCT Number : NCT02547038

Date of the document : 01 02 2019 (MM/DD/YYYY)

ABSTRACT

Background: With the rising prevalence of antimicrobial resistance, the failure rate of the standard triple therapy has declined to unacceptable level (<80%) worldwide. A 14-day hybrid therapy invented by our study group appears very promising in *H. pylori* eradication, achieving excellent eradication rates of 99% and 97% according to per-protocol and intention-to-treat analyses, respectively. Recently, we demonstrated that the eradication rate of reverse hybrid therapy was higher than that of standard triple therapy. However, whether reverse hybrid therapy achieves a higher eradication rate than bismuth quadruple therapy remained unanswered.

Aims: The aims of this randomized controlled trial are (1) to compare the efficacies of reverse hybrid therapy and bismuth quadruple therapy, (2) to investigate the host and bacterial factors predicting the treatment outcomes of the two eradication regimens.

Methods: Consecutive 352 *H. pylori*-infected subjects are randomly assigned to receive either a 14-day reverse hybrid therapy or a 14-day bismuth quadruple therapy. On recruitment, blood sampling for genotyping of *CYP2C19* is carried out, and antibiotic susceptibility of *H pylori* strains will be checked. Subjects are asked to return at the end of the 2nd week to assess drug compliance and adverse events. *H pylori* status will be re-assessed at week 6 after the end of anti-*H. pylori* therapy. Finally, the rates of eradication, adverse events and compliance will be compared between groups by chi-square test, and the host and bacterial factors influencing each efficacy of the regimen are assessed by multivariate analysis.

Introduction

Helicobacter pylori (*H. pylori*) infection is the principal cause of chronic gastritis, gastric ulcer,

duodenal ulcer, gastric adenocarcinoma and gastric mucosa-associated lymphoid tissue lymphoma.¹

In most international guidelines,²⁻⁴ 14-day standard triple therapy is still recommended as a choice

of treatment for the first-line therapy of *H. pylori* infection, especially in areas of low

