clarithromycin resistance ($\leq 15\%$). However, the eradication rates of standard triple therapy have declined to less than 80% in most countries because of the rising prevalence of clarithromycin resistance.⁵ Several strategies including bismuth-containing quadruple therapy and non-bismuth-containing quadruple therapy have therefore been proposed to increase the eradication rate.^{5,6}

In the Maastricht V/Florence Consensus Report,³ bismuth quadruple therapy is the treatment of choice for the first-line therapy of *H. pylori* infection in areas of high clarithromycin resistance ($> 15\%$) and an alternative in areas of low clarithromycin resistance. In the recent American College of Gastroenterology (ACG) guideline, it is also recommended as a first-line treatment for *H. pylori* infection.⁴ However, the complicated administration of bismuth quadruple therapy easily reduces the adherence of patients, and the complex therapy is associated with a high frequency of adverse events.^{7,8}

Hybrid therapy developed by Hsu et al. in 2011 consists of a dual therapy with a proton pump inhibitor (PPI) and amoxicillin for 7 days followed by a quadruple regimen with a PPI, amoxicillin, clarithromycin and metronidazole for 7 days.⁶ It achieved an eradication rate of 97.4% by intention-to-treat (ITT) analysis and 99.1% by per-protocol (PP) analysis in Taiwan.⁶ Subsequent randomized controlled trials demonstrated that 14-day hybrid therapies were comparable or more effective than 10-day sequential therapies.^{9,10} A recent large multicentre randomized controlled trial documented that 14-day hybrid and 14-day concomitant therapies had comparable efficacy in the treatment of *H. pylori* infection, and both could cure more than 90% of patients with *H. pylori* infections in areas of high clarithromycin and metronidazole resistance.¹¹ Currently, it is a recommended first-line

treatment choice in the ACG guideline⁴ and the Taiwan *Helicobacter pylori* Consensus Report.¹²

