However, hybrid therapy requires additional two antibiotics in the last 7 days, which can confuse patients and may dampen enthusiasm for its use. Reversing the sequence of drug administration (a quadruple regimen followed by a dual regimen) can simplify hybrid therapy. The aims of this randomized controlled trial are (1) to compare the efficacies of reverse hybrid therapy and bismuth quadruple therapy, (2) to investigate the host and bacterial factors predicting the treatment outcomes of the two eradication regimens.

PATIENTS & METHODS

Study population

The open-labeled trial is conducted at the Kaohsiung Veterans General Hospital and Kaohsiung Medical University Hospital in Taiwan in accordance with the principles of good clinical practice from the Declaration of Helsinki. The study protocol will be approved by the Ethics Committees of the Kaohsiung Veterans General Hospital and the Kaohsiung Medical University Hospital. All patients give written informed consent before participating in the study.

We will recruit 352 patients to the study if they meet the following criteria: they are adult patients aged ≥ 20 years and have *H pylori* infection. The exclusion criteria include The exclusion criteria include (1) previous *H pylori*-eradication therapy, (2) patient with allergic history to the medications used, (3) patients with previous gastric surgery, (4) coexistence of serious concomitant illness (for example, decompensated liver cirrhosis, uremia), and (5) pregnant

women.

Randomization and treatment

This is a randomized controlled trial. Eligible *H. pylori*-infected subjects are randomly assigned to a 14-day reverse hybrid therapy (a 7-day quadruple regimen with pantoprazole 40 mg twice daily, amoxicillin 1 g twice daily, clarithromycin 500 mg twice daily, and metronidazole 500 mg twice daily, followed by a 7-day dual regimen with pantoprazole 40 mg twice daily and amoxicillin 1 g twice daily) or a 14-day bismuth quadruple therapy (pantoprazole 40 mg twice daily, bismuth tripotassium dicitrate 120 mg, and tetracycline 500 mg four times daily for 14 days). All drugs are taken one hour before breakfast and dinner. Patients with peptic ulcers in initial endoscopy receive an additional 4-week pantoprazole therapy (40 mg orally once daily), while patients with symptomatic gastritis only take additional four-weeks of antacid.

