To determine the independent factors affecting the treatment response, Host and bacterial parameters are analyzed by univariate analysis. These variables include the following: age (<60 or \geq 60 years), gender, history of smoking, history of alcohol consumption (<80 g/day or \geq 80 g/day), ingestion of coffee (<1 cup/day or \geq 1 cup/day), ingestion of tea ((<1 cup/day or \geq 1 cup/day), coexistence of a systemic disease (yes or no), previous history of peptic ulcer disease, endoscopic appearance (ulcer or gastritis), CYP2C19 polymorphism, drug compliance (good or poor), and antibiotic susceptibility. Those variables found to be significant by univariate analysis are subsequently assessed by a stepwise logistic regression method to identify independent factors for eradication outcome.

REFERENCES

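### Aim 2 relies on unqualified stepwise logistic regression with no safeguard if failures are few, so a strong predictor may have no finite odds ratio in a per-regimen analysis

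*Combined protocol and SAP*

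**What the plan says.** The second of the two stated aims is to find host and bacterial factors that predict outcome. The last paragraph of the Statistical analysis section lists 12 candidate factors, screens them one at a time, and has those that reach significance "assessed by a stepwise logistic regression method to identify independent factors for eradication outcome". It gives no estimator, entry or removal criterion, minimum number of failures, or rule for a factor level without failures. Fisher's exact test is available for comparing the major outcomes between groups, but the regression has no counterpart to it.

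The unit of analysis is open. The Abstract says "the host and bacterial factors influencing each efficacy of the regimen are assessed by multivariate analysis", which points to a model for each regimen. The body text does not say whether the arms are pooled, or whether the model uses the ITT or PP population.

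On the likely number of failures, the Study population section says "We will recruit 352 patients to the study". The Introduction says of the original hybrid regimen: "It achieved an eradication rate of 97.4% by intention-to-treat (ITT) analysis and 99.1% by per-protocol (PP) analysis in Taiwan". It also reports a multicentre trial of hybrid and concomitant therapies in which "both could cure more than 90% of patients with" the infection. For reverse hybrid therapy the Abstract says only that "the eradication rate of reverse hybrid therapy was higher than that of standard triple therapy". No numerical rate is given for bismuth quadruple therapy.

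**The concern.** Logistic regression draws its information from the less common outcome, here treatment failure. When every failure falls in one level of a factor, the likelihood keeps rising as the coefficient grows and no finite maximum-likelihood estimate exists. Software stops at an arbitrary large coefficient with a huge standard error, and the Wald P value is close to 1 however strong the association.

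This differs from the familiar problem of stepwise selection picking up noise. It would remain if all factors were prespecified and nothing were selected. It also falls mainly on strong predictors, which aim 2 exists to find. Such a factor could pass the univariate screen with a very small P value and then be reported with an infinite odds ratio or, under Wald-based removal, be discarded as not independent.

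**Working it through.** **Inputs.** From the documents: 352 patients, two arms, 12 candidate factors, significance at P<0.05, and eradication of 97.4% (ITT), 99.1% (PP) and more than 90% for hybrid therapy. Assumed: 1:1 allocation (176 per arm), bismuth quadruple eradication of 80% to 97.4%, and the factor prevalences and true odds ratios shown below. The plan states no expected number of failures for aim 2, so there is no figure to reproduce.

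**Step 1. Expected failures** = n × (1 − eradication rate).

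| Eradication | One arm (176) | Both arms at this rate (352) | Failures per candidate factor, arm / pooled |
|---|---|---|---|
| 99.1% | 1.6 | 3.2 | 0.1 / 0.3 |
| 97.4% | 4.6 | 9.2 | 0.4 / 0.8 |
| 95% (assumed) | 8.8 | 17.6 | 0.7 / 1.5 |
| 90% | 17.6 | 35.2 | 1.5 / 2.9 |

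With one arm at 97.4% and the bismuth arm at 95%, 90% or 80%, the pooled total is 4.6 + 8.8 = 13.4, 4.6 + 17.6 = 22.2, or 4.6 + 35.2 = 39.8. Pooled ITT totals of about 9 to 40 are therefore all compatible with the documents.

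**Step 2. What maximum likelihood does with an empty cell.**

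- 9 failures among 70 exposed, 0 among 282 unexposed. The odds ratio is (9 × 282)/(61 × 0), which is not finite. Fisher P = 3.2e-7 and likelihood-ratio P = 4e-8, but after 20 iterations the coefficient is about 19 and still growing, with Wald P = 0.99. The standard error (in the thousands) depends only on where the iteration stops.
- 5 of 26 against 0 of 150, a one-arm example. Fisher P = 4.9e-5, Wald P = 0.995.
- 8 of 53 against 1 of 299. A single failure in the other level removes the problem: Wald P = 0.0002.

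**Step 3. How often this would happen.** Trials were simulated with a two-level factor. The table gives the share of factors passing a univariate Fisher P<0.05 whose maximum-likelihood odds ratio is infinite.

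| Setting | Failures | Prevalence | Share infinite |
|---|---|---|---|
| One arm, true OR 8 | 4.6 | 15% / 30% / 50% | about 20% / 50% / 90% |
| One arm, true OR 8 | 8.8 | 15% / 30% / 50% | about 2% / 14% / 51% |
| One arm, true OR 8 | 17.6 | 15% / 30% / 50% | about 0% / 1% / 11% |
| Pooled, true OR 10 | 9.2 | 10% / 20% / 50% | about 1% / 7% / 54% |
| Pooled, true OR 10 | 22 | 10% / 20% / 50% | about 0% / 0% / 11% |
| Pooled, true OR 10 | 35 | 10% / 20% / 50% | about 0% / 0% / 2% |

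These shares are conditional on passing the screen. In one arm with 4.6 failures and prevalence 40%, a factor with true OR 5 passes 26% of the time and 63% of those passes are infinite, so the unconditional figure is 0.26 × 0.63 = 16%. With true OR 20 it is 0.57 × 0.84 = 48%.

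**Step 4. The same tables under Firth's penalty.** With one two-level factor, the Firth estimate equals adding 0.5 to each cell. For 9/70 against 0/282, OR = (9.5 × 282.5)/(61.5 × 0.5) = 87, with 95% profile interval 10.8 to about 11,300 and P = 1e-7. For 5/26 against 0/150, OR = (5.5 × 150.5)/(21.5 × 0.5) = 77. The estimates and tests are usable, but the first interval shows how little is known about the size of the effect.

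**The case against.** The strongest reply is that failures may not be scarce. A reader might infer from the Introduction that the trial will see only a handful. The documents do not support that: the 97.4% and 99.1% come from one study of the earlier hybrid regimen, the same section also quotes more than 90%, and no rate is given for bismuth quadruple therapy. The ITT rule counts unknown outcomes as failures, and the Introduction expects poorer adherence on bismuth therapy. Both could add events. With 22 to 35 pooled failures an infinite odds ratio is uncommon, at most 11% even for a true odds ratio of 10. This stands, and it makes the concern conditional.

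A reader might also infer that the affected factor will be lost. The plan does not say that. It names no Wald test, and under likelihood-ratio removal the factor in the 9/70 against 0/282 example would stay (chi-square about 30 on 1 degree of freedom). The univariate screen would also flag it. An infinite odds ratio is visible on the printout, so an analyst need not be misled. This stands too. What remains in any case is that the adjusted odds ratio and its Wald interval cannot be used.

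Finally, maximum likelihood is inferred rather than stated, aim 2 is not among the listed primary or secondary outcome variables, and penalisation is not the only remedy. These points lower the severity. They do not supply a safeguard, and the plan cannot exclude the sparse case because it fixes neither the unit of analysis nor the population.

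**Conclusion.** The point holds conditionally. In a per-regimen analysis with eradication near the quoted hybrid rates, an arm rests on about 2 (PP) to 5 (ITT) failures. Roughly 20% to 90% of strong factors that pass the screen would then have no finite odds ratio, for true OR 8 and prevalence 15% to 50%. At 90% eradication an arm has up to about 18 failures and the share falls to about 0% to 11%. In a pooled model near 90% it is about 2% or less at true OR 10.

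This rests on 1:1 allocation, on ordinary maximum likelihood as the meaning of unqualified logistic regression, and on assumed prevalences and odds ratios. Loss of a factor from the model further requires Wald-based removal. Severity is minor to moderate: only aim 2 is affected, and the primary comparison of eradication rates is not.

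**What to change.** In the last paragraph of the Statistical analysis section, specify that the aim-2 models are fitted by Firth-penalised logistic regression, that factors are judged by penalised likelihood-ratio tests, and that odds ratios carry profile penalised-likelihood confidence intervals in place of Wald statistics. Tabulate the number of failures in each level of each factor beside the odds ratios. The same paragraph should say whether the models are per regimen or pooled, and ITT or PP, so that the expected number of failures can be judged.

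The cost is a wording change and possibly software beyond the SPSS version named. Odds ratios shrink slightly toward 1 when failures are plentiful. When failures are few the intervals remain very wide, because the method restores a finite estimate and a usable test without adding information. Naming it beforehand avoids an improvised choice after a divergent fit has been seen.
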